6.13. Discontinuation

The investigator should contact the sponsor or its designee and forward appropriate supporting documents for review and discussion prior to discontinuing a subject. All subjects who have received at least one dose of IP should undergo Treatment Discontinuation procedures when treatment is discontinued. The Treatment Discontinuation procedures include AEs, monitoring for progression of AML and SPM, physical examination, vital signs and weight measurements, ECOG performance status, hematology and serum blood chemistry, serum ferritin level, pregnancy test (FCBP only), concomitant medications, therapies and procedures, transfusions administered, disease status assessment, subsequent AML therapies, IP accountability, HRQoL, and healthcare resource utilization.

If a subject is discontinued during a regular scheduled visit, all Treatment Discontinuation procedures should be complete at that visit. If a procedure had been performed within 7 days of the Treatment Discontinuation visit, it does not need to be repeated. For bone marrow aspirate and bone marrow biopsy, if the procedures have been performed within 15 days of Treatment Discontinuation visit, these procedures do not need to be repeated.

The reason for discontinuation will be recorded in the CRF and in the source document for all randomized subjects, regardless of whether they are dosed or not. Reasons for discontinuation are provided in Section 12.

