6.14. Follow-up

All subjects discontinued from protocol-prescribed therapy for any reason will be followed for a period of 28 days following the last dose of IP or until the date of the last study visit, whichever is later, for the collection of AEs, concomitant medications, therapies and procedures, and healthcare resource utilization. Females of childbearing potential should avoid becoming pregnant for 3 months after the last dose of IP and male subjects should avoid fathering a child for 3 months after the last dose of IP.

All subjects discontinued from protocol-prescribed therapy for any reason will also be followed for survival, AML relapse, subsequent AML therapies, and SPM every month for the first year following Treatment Discontinuation and every three months thereafter until death, lost to follow-up, withdrawal of consent for further data collection, or study closure. Documentation such as laboratory or pathology reports, bone marrow and/or peripheral blood reports supporting the AML relapse should be requested and collected. The investigator must make every effort to obtain information regarding the subject's survival status before determining the subject is lost to follow-up. Survival follow-up can be performed via the telephone.

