12. DISCONTINUATIONS

The following events are considered sufficient reasons for discontinuing a subject from the IP / treatment:

- Disease relapse
Subjects will be discontinued from treatment when they meet the following criteria.
 - Appearance of > 15% blasts in the bone marrow or peripheral blood; and
 - The above occurrence should be attributed to relapse following CR/CRi, and not attributable to any other cause (eg, bone marrow regeneration after consolidation therapy or myeloid growth factor administration).
- AE(s)
- Subject withdraws from active treatment but continues follow-up
- Subject becomes eligible (per Investigator) for allogeneic bone marrow or stem cell transplantation during treatment period
- Death
- Lost to follow up
- Protocol violation

Prior to discontinuing IP treatment for a subject assessed to have disease relapse, the Investigator may contact the Medical Monitor and forward appropriate supporting documents for review and discussion.

The reason for discontinuation will be recorded in the CRF and in the source documents.

All subjects discontinued from protocol prescribed treatment for any reason should undergo Treatment Discontinuation procedures including pregnancy test for FCBP. Additionally, all subjects discontinued from protocol prescribed treatment will be followed for a period of 28 days following the last dose of IP or until the date of the last study visit, whichever is later, for the collection of adverse events. Discontinued subjects will not be replaced.

During the follow-up period, all subjects should be followed every month for the first year and then every 3 months thereafter until death for collection of information on survival, AML relapse, monitoring for SPM and subsequent AML therapies, unless the subject has specifically withdrawn consent from further follow-up. Documentation such as laboratory or pathology reports, bone marrow and/or peripheral blood reports supporting the AML relapse will be requested and collected. The Investigator must make every effort to obtain information regarding the subject's survival status before determining the subject is lost to follow-up.

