### 11.2.2. Sensitivity Analysis

The primary efficacy analysis, as described above, will be repeated using the mITT population as a sensitivity analysis.

To assess the potentially confounding effects of other therapy received subsequent to the study treatment, the following additional sensitivity analysis will be performed.

1. Censoring for the use of any subsequent therapy (including post-treatment transplant) for AML. For this analysis, subjects who received any subsequent therapy for AML following discontinuation from their study drug will be censored on the earlier of first subsequent therapy date, or transplant date, regardless of their survival status at the time of the final analysis.
2. Censoring for the use of disease modifying subsequent AML therapy, which is defined as any subsequent AML therapy that is not hydroxycarbamide.
3. Censoring for post-treatment transplant. For this analysis, subjects who received post-treatment transplant will be censored at the time of the transplant.

These modified time to death endpoints will be based on the ITT population and analyzed using the same methods described previously for the primary efficacy endpoint. In addition, based on the 13 April 2018 Type C Guidance meeting with the Agency on the analysis issues with subsequent therapy, the following analyses will be performed to further investigate impacts of subsequent AML therapy on the overall survival. The following methods are planned:

- Cox proportional hazard model with covariates adjustment will include, but not limited to, subsequent AML therapy (time-varying (yes or no)); treatment-by-subsequent AML therapy interaction; baseline characteristics such as age, ECOG score, cytogenetic risk status, CR/CRi status at randomization, etc. The covariates included in the final Cox model will be selected using stepwise variable selection procedure.
- Inverse probability of censoring weighted (IPCW) method. The IPCW modeling approach was introduced by Robins et al and estimates hazard ratios that are valid in the

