presence of informative censoring at start of subsequent therapy. The method adjusts for subsequent therapy by recreating the population that would have been evaluated in the absence of any subsequent therapy by weighting the follow-up for those subjects who did not receive additional therapy in order to account for the follow-up of subjects who did receive subsequent therapy that has been (informatively) censored. The weights are determined by matching demographic and baseline characteristics as well as post randomization clinical factors for subjects who did and did not receive subsequent therapy. Baseline covariates include the following: age, sex, ECOG score, cytogenetic risk status at diagnosis, prior history of MDS, geographic region, CR/CRi first achieved after induction, time to first achieving CR/CRi, CR/CRi status at randomization, MRD status at randomization, with or without consolidation, # of consolidation cycles received, platelet and ANC counts. Post randomization factors include platelet count, ANC, binary indicator of history of grade 3 or 4 AE, binary indicator of occurrence of a grade 3 or 4 since last visit, time since last visit (months), bone marrow blast %, and ECOG score. Each subject is weighted equal to the inverse probability of not receiving additional treatment. Adjusted HRs for the treatment effect are then estimated from Cox regression models with adjustment for subsequent therapy (i.e., censoring at time of subsequent therapy), both with and without further adjustment for baseline covariates.

- Regression based imputation analysis method proposed by Luo, X. et al that allows for inferences about the treatment effect in the presence of confounding due to additional therapy received subsequent to the study treatment. This method provides adjusted estimates of the KM survival curves, which allows for comparisons using the log-rank test and the calculation of an adjusted HR and associated confidence intervals.

At the final analysis, the assumption of proportional hazards will be tested by a time-dependent Cox model with interaction of treatment and time. A figure of hazard function over time will give an instinct idea of hazard trend over time.

If proportional hazard assumption is violated, the following sensitivity analyses will be conducted using ITT population:

1. Restricted mean survival time will be generated and compared between oral azacitidine and placebo arms;

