#### 11.3.1. Key Secondary Endpoint – Relapse-free Survival (RFS)

##### Primary analysis

Relapse-free survival is defined as the time from the date of randomization to the date of documented relapse or death from any cause, whichever occurs first. Subjects who are still alive without documented relapse, or who were lost to follow-up or withdrew consent without documented relapse, will be censored at the date of their last bone marrow assessment. Relapse is defined according to the IWG AML response criteria. See Appendix 17.7 for definitions of response categories. Documented relapse is defined as, the earliest date of the following

- $\geq 5\%$  bone marrow blasts (myeloblasts) from Central Pathology report, or
- appearance of  $> 0\%$  blasts in the peripheral blood with a later bone marrow confirmation (bone marrow blast [myeloblasts]  $\geq 5\%$ ) within 100 days, or
- at least 2 peripheral blasts  $\geq 5\%$  within 30 days.

Peripheral blasts reported from both Central Pathology and Central lab will be considered. Subjects who withdrew for any reason or received another therapy for AML without documented relapse will be censored on the date of their last bone marrow assessment, prior to receiving any other therapy for AML. Subjects who are still on treatment at the time of study closure without documented relapse will be censored on the date of their last bone marrow assessment. These rules are based on FDA guidance for cancer trial endpoints [REDACTED], and table 2 specifies the application of the guidance for various common situations for the calculation of RFS.

**Table 2** Primary Censoring Rules for RFS

Situation	Derivation Rules	Situation Outcome

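### The IPCW weight model for overall survival lists neither documented relapse nor off-study-drug status, so the validity claimed for its hazard ratio is not assured

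*SAP*

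**What the plan says.** SAP 11.2.2 presents IPCW as a way to recover the survival comparison that would have been seen without subsequent AML therapy. It says the resulting hazard ratios stay valid when censoring at therapy start is informative. The weights are defined thus: "Each subject is weighted equal to the inverse probability of not receiving additional treatment". The time-varying inputs begin "Post randomization factors include platelet count, ANC, binary indicator of history of grade 3 or 4 AE", continue with a grade 3 or 4 event since the last visit, and end "time since last visit (months), bone marrow blast %, and ECOG score". A set of baseline covariates is added. No rule is given for carrying a factor forward after treatment stops, and the SAP does not say whether a telephone contact counts as a visit.

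The companion simple-censoring analysis in the same section fixes the sequence of events: "subjects who received any subsequent therapy for AML following discontinuation from their study drug will be censored".

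The protocol lists relapse among the reasons for stopping treatment (section 12), with the blast criterion "Appearance of > 15% blasts in the bone marrow or peripheral blood; and" and a second condition on attribution. After stopping, subjects "will also be followed for survival, AML relapse, subsequent AML therapies, and SPM every month for the first year following Treatment Discontinuation" (protocol 6.14); later contacts are quarterly. Reports supporting a relapse are to be requested.

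**The concern.** IPCW removes the bias from censoring at therapy start only if the weight model contains the factors that drive both starting therapy and the risk of death. In this disease relapse is the obvious one, and being off study drug is a precondition by the SAP's own definition. Neither is in the list as such. The listed clinical factors are measured mainly on treatment, so they can be out of date when the decision to start therapy is made.

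At stake is the credibility of one adjusted hazard ratio. The SAP ties this group of analyses to a regulatory meeting on subsequent therapy, so it is likely to be read closely.

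**Working it through.** **1. What the weight model can see once treatment stops** (protocol Table 1, 6.13, 6.14; SAP 11.2.2)

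| Item | In listed model | Last scheduled |
|---|---|---|
| Marrow blast % | yes | Treatment Discontinuation visit |
| Platelets, ANC | yes | Treatment Discontinuation visit |
| ECOG | yes | discontinuation in 6.13; blank there in Table 1 |
| Grade 3/4 AE | yes | 28 days after last dose or last study visit, whichever is later |
| Time since last visit | yes | visit undefined off treatment |
| Documented relapse | no | followed monthly, then every 3 months |
| Off study drug | no | date known |

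**2. Which relapses the list captures.** Under SAP 11.3.1 relapse can be documented by marrow blasts of at least 5%, by peripheral blasts confirmed in marrow within 100 days, or by two peripheral readings of at least 5% within 30 days. "Peripheral blasts reported from both Central Pathology and Central lab will be considered". Marrow blast % captures the marrow-based routes on treatment or at the discontinuation visit. It can miss relapse met on peripheral blasts alone, and relapse after a stop for another reason.

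**3. Why a missed relapse matters for the weight.** A subject still untreated after k months has an unstabilised weight of 1/(1-p)^k, where p is the monthly chance of starting therapy. Assume p = 0.20 after relapse and 0.003 before it. After 6 months off drug the weight is 1/0.80^6 = 3.81 if relapsed and 1/0.997^6 = 1.02 if not. A model that cannot tell these subjects apart gives them the same weight, and under-represents relapsed patients who would have died untreated. At p = 0.35 the weight is 1/0.65^6 = 13.3, which is where instability begins to matter.

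**4. The plan's own figures.** The documents give no figure for IPCW. The design reproduces: 4(1.960 + 1.282)²/(ln 0.70)² gives 331 deaths against 330 stated, and power at 330 deaths is 0.900.

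**5. Illustrative simulations.** Every rate below is an assumption; none is in the documents. *Fuller* means the listed factors plus relapse and off-drug status.

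Model A: 30,000 subjects, 60 months. Relapse 5.5% per month (HR 0.70, frailty SD 0.5). Death 0.6% per month before relapse and 13% after. Therapy only off drug, 20% per month after relapse and 0.3% before, halving the death hazard. Non-relapse stops 1-3% per month on azacitidine and 0.6-1% on placebo.

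Model B: ten data sets of 20,000 per setting, last values carried forward after stopping, stabilised weights by arm, 53-68% starting therapy. The two listed-factor values are for telephone contacts counting as visits / only clinic visits counting.

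| Setting | True HR | Listed factors | Fuller | Simple censoring |
|---|---|---|---|---|
| A, more stops on azacitidine | 0.80-0.81 | 0.73-0.75 | 0.82-0.83 | 0.84-0.85 |
| A, equal stopping | 0.79 | 0.80 | 0.79 | not reported |
| A, therapy 35% per month | 0.78 | 0.77 | 0.83 | not reported |
| B, base | 0.767 | 0.700 / 0.636 | 0.750 | 0.756 |
| B, AE stops 5% v 1% per month | 0.766 | 0.642 / 0.530 | 0.770 | 0.746 |
| B, AE stops 2% in both arms | 0.761 | 0.723 / 0.683 | 0.759 | 0.772 |
| B, slower switching | 0.768 | 0.729 / 0.750 | 0.765 | 0.750 |

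In B the Monte Carlo standard errors on the log scale are 0.004-0.006 for the truth, 0.009-0.047 for the listed factors and 0.006-0.014 for the fuller model. No such errors are available for A.

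A third model (C), with more non-relapse stops on azacitidine, gave 0.75-0.78 for the listed factors and 0.82-0.84 for the fuller model, against a true 0.82-0.85. At the trial's 460 subjects its root mean squared error (fuller v listed) was 0.15 v 0.19 in the base case, 0.16 v 0.16 with equal stopping, and 0.23 v 0.24 with 35% monthly switching.

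**6. Scale.** With all 330 deaths counted, SE(log HR) is about 2/√330 = 0.110. The shift in A, from 0.805 to 0.74 at mid-range, is ln(0.805/0.74) = 0.084 on the log scale, below one standard error. Censoring and weighting would enlarge that error.

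**The case against.** A reader might infer that the model ignores relapse altogether. It does not. Marrow blast % is listed, at least 5% marrow blasts is the first route to documented relapse, and a marrow is due at discontinuation unless one was done within the preceding 15 days. Time since last visit may also partly stand in for being off drug. The SAP does not restrict marrow blast % to scheduled samples, so follow-up reports could feed it, and the verb introducing the list need not mean that it is complete. These points narrow the gap without closing it: nothing else is pre-specified, and no data-source or carry-forward rule says that follow-up relapse will be used.

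A reader might also infer that the error favours azacitidine. The documents give no stopping, relapse or switching rates by arm, so direction cannot be read from them. The simulations show only that it can go that way if non-relapse stops are more frequent on azacitidine.

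The fuller model is not uniformly better. In A at 35% monthly switching it was further from the truth (0.83 against 0.78) than the listed factors (0.77). That setting is not extreme. Treating therapy and death as competing rates and ignoring frailty, the share of relapsed subjects treated is 0.431/(0.431 + 0.139) = 76%, against 0.223/(0.223 + 0.139) = 62% at 20% per month. This objection stands as a reason to report both models and the weights. The trial-size results in C show no detectable loss from the fuller model; I would not read them as proof of a gain. The models also disagree on simple censoring: too high in A, close to the truth in B.

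**Conclusion.** The point holds as a cheap improvement. As listed, the weight model can miss relapse after a non-relapse stop and relapse met on peripheral blasts alone, and it has no term for the off-drug state that precedes subsequent therapy. The SAP's statement of validity under informative censoring is therefore not assured.

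On assumed rates with more non-relapse stops on azacitidine, the listed factors put the hazard ratio about 0.06 too low in A, and 0.12 to 0.24 too low in B at the most unequal stopping. With equal stopping the gap was 0.01 in the other direction in A and 0.04 in B, or 0.08 in B if only clinic visits count. What is shown is the possibility of bias, not its size or sign in this trial.

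Nor do the documents support any inference that the main survival result is in doubt. The confirmatory test is the ITT stratified log-rank test, which does not use these weights. IPCW is one of several supportive analyses, alongside three censoring rules, a time-varying Cox model and a regression-based imputation.

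**What to change.** In SAP 11.2.2:

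- Add time-varying documented relapse to the weight model, including relapse reported in follow-up, and off-study-drug status.
- Estimate the probability of starting therapy only in off-drug person-time, and define the off-drug date. The candidates are last dose, last dose plus 14 days (the SAP 9.1 treatment end date) and the discontinuation visit. The choice should not leave therapy starts inside time counted as on drug.
- State the carry-forward rule and whether telephone contacts are visits.
- Use stabilised weights, pre-specify the truncation, and report the weight distribution.
- Show the result from the currently listed factors alongside.

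The cost is SAP wording and modest programming; the relapse and therapy data are already collected. The downside is larger, more variable weights if most relapsed subjects start therapy, which is why both models should be shown.

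Separately, protocol 6.13 lists "ECOG performance status, hematology and serum blood chemistry, serum ferritin level" among the Treatment Discontinuation procedures, while Table 1 and its copy in SAP 17.3 leave ECOG blank at that visit. The passages should be reconciled. This is a schedule point and cannot recover values not recorded.

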### **4.4. Sample Size Determination**

The equality of OS curves will be compared between the oral azacitidine and placebo treatment arms using a stratified log-rank test. Assuming a median OS of 16 months in the placebo treated group ([REDACTED]), a median OS of 22.9 months in the oral azacitidine treated group (43% improvement), and a study duration of 60 months with a drop-out rate of 5% from both treatment arms, over the duration of the study, this design requires 330 deaths and approximately 460 subjects (230 per treatment arm) to be randomized in order to achieve at least 90% power to detect a constant hazard ratio of 0.70 and demonstrate a statistically significant difference in OS. It is assumed that the OS distribution is exponential with a constant failure (hazard) rate and that accrual is non-uniform during an accrual period of 36 months with 25% of the subjects accrued during each of the first 2 years of enrollment (50% accrued at 24 months) and the remaining 50%

accrued during the last year of enrollment. Sample size calculations are based on a one-sided alpha of 0.025 with one interim analysis for futility after 30% of the events have occurred.

Sample size was calculated using the East® Version 5.4 software system [REDACTED] [REDACTED]).

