### 11.1. General Statistical Methods

All hypothesis testing will be carried out at the 5% (2-sided) significance level and designed to evaluate the superiority of oral azacitidine relative to Placebo.

The study randomization scheme was stratified according to 4 prognostic features: age at time of induction therapy 55-64 versus  $\geq 65$  years; prior history of MDS: yes versus no; cytogenetic risk status at time of induction therapy: intermediate risk versus poor risk; and received consolidation therapy following induction therapy: yes versus no, resulting in 16 strata. The statistical analyses conducted to compare treatment arms will include methods that are stratified according to the randomization scheme, using the stratification factors as collected in the clinical database (for subject with missing stratification factor, the missing stratification factor value will be imputed by the data entered via the IVRS). Additionally, for primary endpoint OS and key secondary endpoint RFS, the stratified analysis using IVRS data may also be conducted. It is possible that the number of subjects in an individual stratum may be very small. In order to facilitate inferential statistical analysis, if the minimum number of subjects in a stratum is less than 16 (irrespective of treatment arm), then only the 3 stratification variables that result in the largest minimum stratum size will be used for analysis purposes. Analyses will not be stratified by investigative center, as the recruitment for many centers is likely to be very small.

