2. Piecewise cox regression will provide hazard estimates at the following intervals,  $\leq 3$  months,  $3 < \leq 6$  months,  $6 < \leq 12$  months and  $> 12$  months;
3. In the presence of non-proportional and early OS separation, a generalized Wilcoxon test will be utilized to compare survival curves.

To evaluate the impact of censoring in the primary analysis due to subjects who withdrew consent from survival follow-up, a sensitivity analysis of the OS endpoint will be performed. For this analysis, subjects who withdrew consent from survival follow-up will be treated as an event rather than as a censored observation. This sensitivity analysis will be based on the ITT population.

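### For OS, RMST and piecewise hazard ratios depend on a low-powered proportional-hazards pretest, and the Wilcoxon test also on undefined early separation, so the supportive evidence would be selective

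*SAP*

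**What the plan says.** The trial is sized "to detect a constant hazard ratio of 0.70 and demonstrate a statistically significant difference in OS" (SAP 4.4), and SAP 11.2.1 makes the stratified log-rank p-value the primary one. SAP 11.2.2 then deals with the possibility that the hazard ratio is not constant. At the final analysis a Cox model with a treatment-by-time interaction tests proportionality, and a plot shows the hazard over time. What follows is conditional: "If proportional hazard assumption is violated, the following sensitivity analyses will be conducted using ITT population". Three analyses stand under that condition:

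- an RMST comparison between the arms;
- a piecewise Cox model with breaks at 3, 6 and 12 months;
- a third analysis with a further condition of its own: "In the presence of non-proportional and early OS separation, a generalized Wilcoxon test will be utilized to compare survival curves".

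SAP 11.2.2 does not say what result counts as a violation, which function of time enters the interaction, where RMST is truncated, or what counts as early separation. A level for the pretest can only be inferred from SAP 11.1: "All hypothesis testing will be carried out at the 5% (2-sided) significance level".

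Several summaries that do not need proportional hazards lie outside the condition. SAP 11.1 and 11.2.1 give Kaplan-Meier curves, differences in the median and quartiles with 95% CIs, and 1- and 2-year survival. SAP 11.1 adds the difference in those survival rates with its CI.

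**The concern.** If the treatment effect fades or starts late, the single Cox hazard ratio is an average that depends on length of follow-up. RMST is the alternative summary the SAP has chosen for that case. Making it conditional on a significance test means it appears only when the test has enough power to reject, and failing to reject is not evidence of proportionality.

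The Wilcoxon condition raises a separate issue. The test gives more weight to early deaths and runs only when the observed curves separate early. No late-weighted test is planned for the opposite pattern. The supportive p-value would therefore tend to appear where it strengthens the case for the arm with the early benefit, and be absent where it would weaken it. At stake is how balanced the supporting evidence for OS is.

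**Working it through.** **Inputs from the SAP.** Section 4.4 gives: "this design requires 330 deaths and approximately 460 subjects (230 per treatment arm) to be randomized in order to achieve at least 90% power"; hazard ratio 0.70; medians of 16 and 22.9 months; accrual over 36 months (25%, 25% and 50% by year); 60 months in total; 5% drop-out. On alpha it says: "Sample size calculations are based on a one-sided alpha of 0.025 with one interim analysis for futility after 30% of the events have occurred".

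**Assumptions not in the documents.** The pretest is at two-sided 5% (inferred from 11.1). The interaction uses linear or log time. The piecewise hazard ratios are chosen for illustration, placebo survival is exponential, and the analysis is unstratified. Early separation is taken as a 12-month Kaplan-Meier difference that is positive for azacitidine and larger than the 36-month difference.

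**Step 1: reproduce the design.** Schoenfeld: 4 × (1.960 + 1.282)² / (ln 0.70)² = 42.03 / 0.1272 = 330.4, so 331 deaths. Power at 330 deaths: Φ(√330/2 × 0.3567 − 1.960) = Φ(1.280) = 0.8997. Expected deaths at 60 months under the stated accrual, medians and drop-out are 335. The stated figures hold.

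**Step 2: power of the pretest in closed form.** Compare the log hazard ratio in the first and second halves of the deaths, 165 each.

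- SE = √(4/165 + 4/165) = 0.220.
- 50% power needs a ratio of early to late hazard ratios of exp(1.960 × 0.220) = 1.54, for example 0.56 against 0.87.
- 80% power needs exp((1.960 + 0.842) × 0.220) = 1.85, for example 0.51 against 0.95.

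**Step 3: simulation.** 460 subjects, data cut at death 330, 4,000 trials per scenario. The figures are the percentage of trials in which the pretest rejects, that is, in which RMST is reported.

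| OS hazard ratio over time | Linear t | Log t |
|---|---|---|
| *Mild or moderate* | | |
| 1 for 3 months, then 0.65 | 12 | 20 |
| 1 for 6 months, then 0.65 | 23 | 30 |
| 1 for 6 months, then 0.60 | 31 | 41 |
| 0.60 for 12 months, then 0.80 | 17 | 15 |
| 0.55 for 12 months, then 0.85 | 31 | 29 |
| 0.50 for 6 months, then 0.80 | 20 | 28 |
| *Strong* | | |
| 0.55 for 24 months, then 1.0 | 45 | 24 |
| 0.50 to 12 months, 0.75 to 24, then 1.0 | 61 | 48 |
| 0.50 for 12 months, then 1.0 | 67 | 62 |
| 1 for 12 months, then 0.50 | 70 | 60 |
| 1.3 for 6 months, then 0.55 | 73 | 84 |
| 0.40 for 12 months, then 1.0 | 86 | 85 |
| 0.50 for 12 months, then 1.3 | 91 | 88 |

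Under the mild or moderate departures RMST is missing in 100 − 41 = 59% to 100 − 12 = 88% of trials. With a constant hazard ratio of 0.70 the pretest still rejects in 5%.

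**Step 4: where the Wilcoxon test appears** (linear-t pretest and the definition of early separation above).

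| Scenario | Log-rank power | Wilcoxon power | Wilcoxon run |
|---|---|---|---|
| 0.50 for 12 months, then 1.0 | 78.0% | 93.7% | 66.8% |
| 1 for 12 months, then 0.50 | 76.5% | 34.5% | 0.0% |

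It is often run where it is stronger than the log-rank test, and not run where it is weaker.

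**Step 5: error under the null** (20,000 trials, two-sided). Log-rank alone: 5.1%. Log-rank, or Wilcoxon when both conditions are met: 5.4%. Either test chosen freely: 6.9%.

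**The case against.** The strongest reply is that nothing confirmatory depends on these conditions. SAP 11.2.1 fixes the stratified log-rank p-value, SAP 11.1 limits formal inference to OS and then RFS, and everything under the condition is labelled a sensitivity analysis. Specifying conditional sensitivity analyses in advance is a legitimate choice. This stands, and it limits the point to supportive evidence.

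A reader might infer that the OS test is picked after seeing the curves, so that the trial's p-value loses its nominal level. The documents do not support that. Only a supportive test is conditional, and even if its success were counted as a win, step 5 puts the error at 5.4% against 5.1%.

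A reader might also infer that RMST is usually missing when it is needed. That depends on the size of the departure: with linear t the pretest rejects in 61% to 91% of trials in six of the seven strong scenarios. Nor would a changing effect be hidden, because the quantile differences, the 1- and 2-year survival differences and the hazard plot are always produced. Those survival and quantile differences describe single points of the curves, however, and do not replace RMST.

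Finally, the Wilcoxon sentence names no arm, so early separation in favour of placebo would also meet it. It is therefore too strong to say that the condition always helps azacitidine.

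**Conclusion.** The point holds as a minor one. SAP 11.2.2 makes RMST and piecewise Cox conditional on a pretest that, at 330 deaths, detects the mild or moderate departures simulated in only about 12% to 41% of trials. RMST would often be missing in that range, though less often under most strong departures. The Wilcoxon test depends on a further, undefined feature of the observed curves and has no late-weighted counterpart, so its result would appear mainly where it favours the arm with early benefit. The consequence is selective supportive evidence. The primary test, its type I error, the 330 deaths and the 90% power are unaffected.

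The percentages rest on the assumed 5% level, the chosen hazard patterns and the time function. The last matters: a hazard ratio of 0.55 for 24 months and then 1.0 is detected in 45% of trials with linear t and 24% with log t. The Wilcoxon figures also rest on the definition of early separation adopted here. The conditional structure and the missing definitions come directly from the SAP text.

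**What to change.** Amend SAP 11.2.2 before unblinding as follows.

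- Report the OS RMST difference between arms with its 95% CI whatever the pretest shows, at a truncation time fixed in advance, for example 24 and 36 months. Under the sizing assumptions the last subject entered has 60 − 36 = 24 months of potential follow-up, and the half accrued by month 24 have at least 60 − 24 = 36.
- Keep the proportional-hazards test and the piecewise hazard ratios as description, report both in all cases, and state the time function and the level of the test.
- Delete the Wilcoxon sentence, or run the test unconditionally and label it descriptive, preferably beside a late-weighted test.

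The cost is one extra table and a few lines of SAP text. RMST would then be reported in every trial, with no change to the primary test, alpha, number of deaths or power.
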